17.2.2 Multiple Imputation

Multiple imputation will be utilized to impute missing IOP values. The primary efficacy variable is Hour 0 IOP change from baseline assessed at Weeks 4, 12, and 24. However, to gain additional imputation efficiency, multiple imputation with a 2-step approach will be used for imputing missing IOP at Weeks 4, 8, 12, 15, 20, and 24 separately for each treatment group. The first step of multiple imputation will use the Markov Chain Monte Carlo (MCMC) method to impute intermittent missing data to achieve a monotone missing pattern. The second step will be based on a linear regression to impute the missing data. Note that baseline IOP values associated with each eye must not be missing in any of the patients; otherwise, they will be excluded from this analysis. Covariates to be included in the regression will be baseline Hour 0 IOP, race, sex, lens status, and age. The planned number of MIs is 25 and a prespecified seed of “123451” will be used for MCMC and a seed of “123457” for the regression part.

A sample code is shown below for Hour 0 IOP measurements associated with each eye:

```
proc mi data=iop nimpute=25 seed=123451 out=_miint;  
  var baseline week4_hr0 week8_hr0 week12_hr0 week15_hr0 week20_hr0 week24_hr0;  
  by treatment;  
  mcmc chain=single impute=monotone;  
run;  
  
proc mi data=_miint nimpute=1 seed=123457 out=mifull;  
  class race_group sex lens;  
  var race_group sex lens age baseline week4_hr0 week8_hr0 week12_hr0 week15_hr0 week20_hr0  
  week24_hr0;  
  monotone regression (week4= race_group sex lens age baseline/details);  
  monotone regression (week8= race_group sex lens age baseline week4/details);  
  monotone regression (week12= race_group sex lens age baseline week4 week8/details);  
  monotone regression (week15= race_group sex lens age baseline week4 week8 week12/details);  
  monotone regression (week20= race_group sex lens age baseline week4 week8 week12 week15/details);  
  monotone regression (week24= race_group sex lens age baseline week4 week8 week12 week15  
  week20/details);  
  by _imputation_treatment;  
run;
```

17.3 ANALYSIS WINDOWS

[Table 17-1](#) provides an overview of efficacy and safety assessments with visit schedule and analysis window table for by-visit and by-cycle analysis.

Table 17-1 Visit Schedule, Visit Windows and By-Cycle Analysis for Efficacy and Safety Assessments

| Efficacy/Safety Assessments | Visit Schedule | Visit Window for by-visit and Analysis Cycle Analysis |
|---|--|--|
| Hour 0 IOP | Baseline, Day 2, W4, W8, W12,W15, W20,W24,W28,W31,W36,W40,W44, W47,W52, M13, M14,M15,M16,M18, M20,M22, M24/EXIT | Table 17-2 |
| Macroscopic conjunctival hyperemia | Baseline, Day2, W4,W8,W12,W15, W20,W24,W28,W31,W36,W40,W44,W47 ,W52,M13,M14,M15,M16,M18,M20,M22 , M24/EXIT | Table 17-2 |
| BCVA | Baseline, Day 2, W4, W8, W12, W15, w20,W24,W28,W31,W36,W40,W44, W47,W52,M13,M14,M15,M16,M18,M20, M22,M24/EXIT | Table 17-2 |
| Visual field | Baseline, W24,W52,M18,M24/exit | Table 17-4 |
| Specular microscopy | Baseline, W4, W12, W24, W40, W52,M16,M20, M24/Exit | Table 17-3 |
| Biomicroscopy | Baseline, Day2, W4, W8,W12,W15, W20,W24,W28,W31,W36,W40,W44, W47,W52, M13,M14,M15,M16,M18, M20,M22, M24/EXIT | Overall by-cycle summary |
| Gonioscopy/ Angle assessment | Baseline,W4(optional),W8,W12(optional), W15,W20,W24(optional),W28,W31,W36, W40,W44,W47,W52,M13,M14,M15,M16, M18,M20,M22,M24/EXIT | Table 17-2 |
| Pachymetry | Baseline, W4, W12, W24, W40, W52, M16, M20, M24/EXIT | Table 17-3 |
| Optic disc/ Ophthalmoscopy/ Lens assessment | Baseline, W12, W24, W40, W52, M16, M20, M24/EXIT | Table 17-3 |

[Table 17-2](#) presents the visits assigned for by- visit and analysis cycle analyses of the efficacy (Hour 0 IOP), and safety assessments that occur every month (or 2 months after 1-year of follow-up after the first Bim SR administration), including of macroscopic conjunctival hyperemia, best-corrected visual acuity, biomicroscopy, and gonioscopy/angle assessment. [Table 17-3](#) presents the visit assigned for by-visit and analysis cycle that occur every 3 or 4 months, including of specular microscopy, pachymetry and optic disc assessments which occur every 3 or 4 months. [Table 17-4](#) presents the visits assigned for by-visit and analysis cycle analyses of visual filed, ophthalmoscopy, optic disc, and lens assessments which occur every 6 months.

If both scheduled and unscheduled visit occur within a single window, the scheduled visit will be used; and unscheduled visits will be used only if there are no scheduled values available in that window. If multiple visits are eligible for windowing within a single visit window, the scheduled visit closest to target day will be used in the analysis.

If 2 visits are equidistant to the target day, the later visit will be used.

Table 17-2 Visit Windows for By Visit Analysis for Assessments Occurring Every 4 weeks

| Derived Visit | Target Visit Day* | Visit Window* |
|-----------------------------------|---|---|
| Baseline ^a | -1 | ≤ (SLT Date -1) |
| Analysis Cycle 1 | | |
| Cycle 1 SLT Day 1 | 1 | SLT Date |
| Cycle 1 Bim SR Day 1 ^b | Bim SR 1st administration, Day 1 | Bim SR 1st administration, Day 1 |
| Cycle 1 Bim SR Day 2 ^b | Bim SR 1st administration, Day 1 + 1 | Bim SR 1st administration Day 1 + 1 |
| Cycle 1 Week 4 | 25 | [Bim SR 1st administration, Day 1+2, 38] |
| Cycle 1 Week 8 | 53 | [39, 66] |
| Cycle 1 Week 12 | 81 | [67, 91] |
| Cycle 1 Week 15 | 102 | [92,119] |
| Cycle 1 Week 20 | 137 | [120, 150] |
| Cycle 1 Week 24 | 165 | [151, 178] |
| Cycle 1 Week 28 | 193 | [179, 203] |
| Cycle 1 Week 31 | 214 | [204, 231] |
| Cycle 1 Week 36 | 249 | [232, 262] |
| Cycle 1 Week 40 | 277 | [263, 290] |
| Cycle 1 Week 44 | 305 | [291, 315] |
| Cycle 1 Week 47 | 326 | [316, 343] |
| Cycle 1 Week 52 | 361 | [344,373] |
| Cycle 1 Month 13 ^c | 387 | [374,401] |
| Cycle 1 Month 14 | 417 | [402,431] |
| Cycle 1 Month 15 ^c | 447 | [432,461] |
| Cycle 1 Month 16 | 477 | [462,506] |
| Cycle 1 Month 18 | 537 | [507,566] |
| Cycle 1 Month 20 | 597 | [567,626] |
| Cycle 1 Month 22 ^c | 657 | [627,686] |
| Cycle 1 Month 24 | 717 | >686 |
| Analysis Cycle 2 ^d | | |
| Cycle 2 Bim SR Day 1 | 1 | Bim SR 2nd administration, Day 1 |
| Cycle 2 Bim SR Day 2 | 2 | Bim SR 2nd Administration Day 1 + 1 |
| Cycle 2 Week 4 | 29 | [Bim SR 2nd administration, Day 1+2, 42] |
| Cycle 2 Week 8 | 57 | [43, 70] |
| Cycle 2 Week 12 | 85 | [71, 98] |
| Cycle 2 Week 16 | 113 | [99,126] |
| Cycle 2 Week 20 | 141 | [127,154] |
| Cycle 2 Week 24 | 169 | [155, 182] |
| Cycle 2 Week 28 | 197 | [183,210] |
| Cycle 2 Week 32 | 225 | [211, 238] |
| Cycle 2 Week 36 | 253 | [239, 266] |

| | | |
|-------------------------------|--|---|
| Cycle 2 Week 40 | 281 | [267, 294] |
| Cycle 2 Week 44 | 309 | [295, 322] |
| Cycle 2 Week 48 | 337 | [323,350] |
| Cycle 2 Week 52 | 365 | [351, 377] |
| Cycle 2 Month 13 | 391 | [378, 405] |
| Cycle 2 Month 14 | 421 | [406,435] |
| Cycle 2 Month 15 | 451 | [436,465] |
| Cycle 2 Month 16 | 481 | [466,495] |
| Cycle 2 Month 17 | 511 | [496, 525] |
| Cycle 2 Month 18 | 541 | [526,555] |
| Cycle 2 Month 19 | 571 | [556,585] |
| Cycle 2 Month 20 | 601 | > 585 |
| Analysis Cycle 3 ^e | | |
| Cycle 3 Bim SR Day 1 | Bim SR 3rd administration, Day 1 | Bim SR 3rd administration, Day 1 |
| Cycle 3 Bim SR Day 2 | Bim SR 3rd administration Day 1 + 1 | Bim SR 3rd administration Day 1 + 1 |
| Cycle 3 Week 4 | 29 | [Bim SR 3rd administration, Day 1+2, 42] |
| Cycle 3 Week 8 | 57 | [43, 70] |
| Cycle 3 Week 12 | 85 | [71, 98] |
| Cycle 3 Week 16 | 113 | [99,126] |
| Cycle 3 Week 20 | 141 | [127,154] |
| Cycle 3 Week 24 | 169 | [155, 182] |
| Cycle 3 Week 28 | 197 | [183,210] |
| Cycle 3 Week 32 | 225 | [211, 238] |
| Cycle 3 Week 36 | 253 | [239, 266] |
| Cycle 3 Week 40 | 281 | [267, 294] |
| Cycle 3 Week 44 | 309 | [295, 322] |
| Cycle 3 Week 48 | 337 | [323,350] |
| Cycle 3 Week 52 | 365 | [351, 377] |
| Cycle 3 Month 13 | 391 | [378, 405] |
| Cycle 3 Month 14 | 421 | [406,435] |
| Cycle 3 Month 15 | 451 | [436,465] |
| Cycle 3 Month 16 | 481 | > 465 |

* Target days and window definitions from Week 4 and onward are based on the relative days from the date of the Bim SR administration for each cycle.

^a Relative to the date of the SLT administration.

^b Relative to the date of Bim SR 1st administration. If a patient did not receive the first Bim SR, but treated in SLT at Day 1, Bim SR 1st administration, Day 1 will be determined as SLT+ 3 days.

^c Patients who received the second administration of Bim SR at W16 and patients who never received a second administration may skip the visits.

^d Relative to the date of the second Bim SR administration.

^e Relative to the date of the third Bim SR administration and valid for Bim SR 15 µg.

Table 17-3 Visit windows for By Visit and Analysis Cycle for Assessments Occurring Every 3- 4 Months

| Derived Visit | Target Visit Day* | Visit Window* |
|---|--|---|
| Baseline ^a | -1 | ≤ (SLT Date -1) |
| Analysis Cycle 1 | | |
| Cycle 1 SLT Day 1 | 1 | SLT Date |
| Cycle 1 Bim SR 1 st Day 1 ^b | Bim SR 1 st administration, Day 1 | Bim SR 1 st administration, Day 1 |
| Cycle 1 Week 4 ^c | 25 | [Bim SR 1 st administration, Day 1+ 1, 52] |
| Cycle 1 Week 12 | 81 | [53, 122] |
| Cycle 1 Week 24 | 165 | [123, 220] |
| Cycle 1 Week 40 | 277 | [221,318] |
| Cycle 1 Week 52 | 361 | [319,418] |
| Cycle 1 Month 16 | 477 | [419, 536] |
| Cycle 1 Month 20 | 597 | [537, 656] |
| Cycle 1 Month 24 | 717 | >656 |
| Analysis Cycle 2^d | | |
| Cycle 2 Bim SR Day 1 | 1 | Bim SR 2nd administration, Day 1 |
| Cycle 2 Week 4 | 29 | [Bim SR 2nd administration, Day 1+1, 42] |
| Cycle 2 Week 8 | 57 | [43, 70] |
| Cycle 2 Week 12 | 85 | [71, 98] |
| Cycle 2 Week 16 | 113 | [99,126] |
| Analysis Cycle 3^e | | |
| Cycle 3 Bim SR Day 1 | 1 | Bim SR 3rd administration, Day 1 |
| Cycle 3 Week 4 | 29 | [Bim SR 3rd administration, Day 1+1, 42] |
| Cycle 3 Week 8 | 57 | [43, 70] |
| Cycle 3 Week 12 | 85 | [71, 98] |
| Cycle 3 Week 16 | 113 | [99,126] |

* Target days and window definitions from Week 4 and onward are based on the relative days from the date of the Bim SR administration for each cycle.

^a Relative to the date of the SLT administration.

^b Relative to the date of Bim SR 1st administration. If a patient did not receive the first Bim SR, but treated in SLT at Day 1, Bim SR 1st administration Day 1 will be determined as SLT+ 3 days.

^c Optic disc assessment will not occur at Week 4. The lower bound of visit window at Week 12 will be Bim SR 1st administration, Day 1+2.

^d Relative to the date of the second Bim SR administration. The visits for Cycle 2 will continue all the way to Month 20. Use the same target day and window as in [Table 17-2](#).

^e Relative to the date of the third Bim SR administration and valid for Bim SR 15 µg. The visits for Cycle 3 will continue all the way to Month 16. Use the same target day and window as in [Table 17-2](#).

Table 17-4 Visit windows for By Visit Analysis for Assessments Occurring Every 6 Months

| Derived Visit | Target Visit Day | Visit Window |
|---|--|---|
| Baseline ^a | -1 | ≤ (SLT Date -1) |
| SLT/Sham SLT Administration Day 1 | 1 | SLT Date |
| Cycle 1 Bim SR 1 st Day 1 ^b | Bim SR 1 st administration, Day 1 | Bim SR 1 st administration, Day 1 |
| Week 24 | 165 | [Bim SR 1 st administration, Day 1+1, 267] |
| Week 52 | 361 | [268, 451] |
| Month 18 | 537 | [448, 627] |
| Month 24 | 717 | >627 |

^a Relative to the date of the SLT treatment.

^b Relative to the date of Bim SR 1st implant. If a patient did not receive the first Bim SR, but treated in SLT at Day 1, Bim SR 1st administration, Day 1 will be determined as SLT+ 3 days.

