7.6 Interim Analyses

No interim analyses are planned.

8. Study Visit Schedule and Procedures

Patients who complete all study treatments will have up to 28 visits and 5 phone calls. The schedule includes the following:

- Screening (up to 28 days); Washout period of up to 56 days for both eyes; and Baseline visit (up to 3 days)
- SLT treatment (Day 1) and phone call (Day 2)
- Bimatoprost SR Cycle 1 administration (Day 4); Cycle 1 Day 2 safety visit; Cycle 1 Day 4 and Week 2 phone calls; and follow-up study visits at Weeks 4, 8, 12, and 15

- Bimatoprost SR Cycle 2 administration (to occur at Week 16 for all patients who meet retreatment criteria); Cycle 2 Day 2 safety visit; and Cycle 2 Day 4 and Week 2 phone calls
 - Patients who do not receive Cycle 2 administration at Week 16 will not attend the Cycle 2 Administration Day visit on Week 16, or the Day 2 Safety or Day 4 and Week 2 phone calls associated with administration at Week 16. For these patients, Cycle 2 may be performed at the investigator's discretion during an unscheduled visit after Week 16 and prior to the Month 12 visit if the retreatment criteria are met; in this case, inadequate control of IOP should be confirmed at another scheduled or unscheduled visit prior to initiation of Cycle 2. All Cycle 2 visits will apply at the time of the Cycle 2 administration.
- Follow-up visits at Weeks 20, 24, 28, 31, 36, 40, 44, 47, and 52; and Months 13, 14, 15, 16, 18, 20, 22, and 24/Exit
 - Regardless of the timing of Cycle 2 administration, all regularly scheduled visits should be completed. Cycle 2 visits should be scheduled such that the Administration Day and the Day 2 Safety Visit do not occur on the day of a regularly scheduled study visit. However, if the Cycle 2 Day 4 or Week 2 Phone Calls overlap with a regularly scheduled visit, perform the regularly scheduled visit.

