8.4.3.8 Cycle 2: Day 2 (Cycle 2 Safety Visit)

The following procedures are performed on Cycle 2 Day 2:

- Collection of adverse events
- Collection of concomitant medications and procedures
- Vital signs (at rest \geq 5 minutes)

The following procedures should be performed in both eyes (procedures in bold should be done in the order shown):

- **Pre-Hour 0 examinations:**
 - Macroscopic conjunctival hyperemia assessment (The examination may also include, [REDACTED])
 - Best-corrected visual acuity
- **Intraocular pressure measurement at Hour 0**
- **Non-contact examination:** The following may be performed at any time after the pre-Hour 0 examinations (including prior to Hour 0 IOP):
 - Biomicroscopy (The examination may also include, [REDACTED])

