  model chg=trt avisitn eye base trt*avisitn
        avisitn*base avisitn*eye/ddfm=kr;
```

```
repeated avisitn*eye/type=un subject=subjid rcorr;  
lsmeans trt*avisitn/diff;  
run;
```

The definitions of variables are:

chg = Hour 0 IOP change from baseline at the primary analysis time points of
Week 4, Week 12, and Week 24

avisitn = Derived analysis visits at Week 4, Week 12, and Week 24

subjid = Subject ID

eye = Variable to indicate primary eye or contralateral eye

trt = Variable to indicate Bim SR treatment or SLT treatment

base = Baseline IOP

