- Time to onset of effect = $(\text{Date of the earliest observation of } \geq 20\% \text{ reduction} - \text{Date of First Treatment}) + 1$

where the Date of First Treatment for SLT is SLT treatment date (Day 1), and the Date of First Treatment for Bim SR 10 μg is the first administration date (Day 4).

For eyes that did not achieve $\geq 20\%$ reduction in IOP at any post-baseline visit, 'Time to onset of effect' will be censored at the date of the latest IOP measurement. Due to large IOP drop on the day immediately after treatment, the IOP values within two days after SLT or Bim SR 10 μg treatment will not be considered for this analysis. Time to onset of effect associated with each eye will be analyzed using Kaplan-Meier method with graphical displays.

10.3.3 Percentage of Bim SR and SLT Eyes Achieving $\geq 15\%$ and $\geq 30\%$ Reductions in IOP by Visit

Number and percent of eyes that have achieved a $\geq 15\%$ reduction in IOP will be summarized by visit and by treatment. Similar summaries for patients achieved $\geq 30\%$ reductions in IOP will be provided.

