Some patients may receive the second Bim SR 10 µg administration after Week 16 and prior to Week 24, thus the time interval between the second Bim SR 10 µg administration and the primary analysis endpoint at Week 24 will be shorter for these patients as compared with patients who received the second Bim SR 10 µg at Week 16. To evaluate any potential impact of this difference in timing of the second administration on Week 24 IOP data from these patients in the primary analysis, additional sensitivity analysis will be conducted by excluding the IOP data at Week 24 for these patients. More specifically, for patients who received flexible administration of the second Bim SR 10 µg beyond the Week 16 visit, the Week 24 IOP assessment will be excluded from the current sensitivity analysis if the second administration date is in the analysis windows for Week 20 or Week 24 and prior to the Week 24 IOP assessment. The MMRM model for the primary efficacy analysis as described in Section 10.1 will be used.

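### Could the Cycle 2 Day 2 pressure reading pass for a Week 15, 20 or 24 efficacy value, since SAP 17.3 does not name the block of Table 17-2 to use?

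*SAP*

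**What the plan says.** The model notes in SAP 10.1 define the visit variable only as "Derived analysis visits at Week 4, Week 12, and Week 24". The windows are in SAP 17.3, Table 17-2. The Cycle 1 block counts days from the first implant: Week 15 has target 102 and window 92–119, Week 20 has 137 and 120–150, and Week 24 has 165 and 151–178. The Cycle 2 block counts from the second implant and has its own Week 24 row, with target 169 and window 155–182. The footnote says that "window definitions from Week 4 and onward are based on the relative days from the date of the Bim SR administration for each cycle".

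If several visits fall in one window, a scheduled visit is preferred to an unscheduled one. Among scheduled visits, "the scheduled visit closest to target day will be used in the analysis", and the later one is used if two are equally distant.

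Protocol 8.4.3.8 lists "Intraocular pressure measurement at Hour 0" among the procedures done in both eyes on Cycle 2 Day 2. When the second implant is given later than Week 16, Protocol Section 8 adds that "All Cycle 2 visits will apply at the time of the Cycle 2 administration".

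SAP 10.3.2, on time to onset, begins its exclusion with the words "Due to large IOP drop on the day immediately after treatment, the IOP values within two days after SLT" and extends it to the implant, for that analysis only. SAP 10.4.5 repeats the primary model without a Week 24 value from a patient retreated after the Week 16 visit "if the second administration date is in the analysis windows for Week 20 or Week 24 and prior to the Week 24 IOP assessment".

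**The concern.** There are two apparent gaps. First, week labels recur across the blocks, and SAP 10.1 does not say which block supplies the primary visits. SAP 11.0 ends Analysis Cycle 1 on the day before the second implant, so a literal reader could conclude that a patient retreated at Week 16 has no Cycle 1 Week 24 at all.

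Second, the first-implant block protects only against the first implant's Day 2 reading, because its Week 4 window opens at Day 1+2. The row that isolates Cycle 2 Day 2 is in the other block. A reading taken the day after the second implant could therefore fall in the Week 15, 20 or 24 window.

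At that visit the Bim SR eye has just received an implant and the SLT eye only a sham. The SAP itself recognises a large next-day drop. A reading picked this way would tend to favour Bim SR, and Week 24 is one of the three visits at which noninferiority must be shown.

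**Working it through.** **The plan's target days.** With SLT on Day 1 and the first implant on Day 4, the first-implant day equals the study day minus 3. The target is then 7 × week − 3. Week 15 gives 102, Week 20 gives 137 and Week 24 gives 165, as in Table 17-2. All 13 Cycle 1 rows from Week 4 to Week 52 agree.

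**Which block is meant.** A second implant at Week 16 (study Day 112) falls on first-implant day 109.
- The regular Week 24 visit is then Cycle 2 day 165 − 109 + 1 = 57, the target of the Cycle 2 Week 8 row.
- The Cycle 2 Week 24 target is first-implant day 169 + 109 − 1 = 277, the Week 40 target.

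The primary lock (SAP 4.0) is triggered by completion of the Week 24 visit, so it cannot rest on a Week 40 reading. Patients never retreated have no Cycle 2 rows. The Hour 0 row of Table 17-1 uses W15, W31, W47 and M22, labels that occur only in the Cycle 1 block. The multiple-imputation list in SAP 17.2.2 includes Week 15. SAP 10.4.5 places the second-implant date inside the Week 20 or 24 window, which makes sense only on the first-implant clock.

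**Week 15 after a Week 16 retreatment.** Inputs are the Week 15 visit at study Day 105 ± 4 and the administration at Day 112 (−2/+4), with Day 2 one day later. This gives 9 × 7 = 63 date combinations.

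| First implant | Week 15 visit (first-implant days) | Cycle 2 Day 2 | Day 2 closer to 102, or tied and later |
|---|---|---|---|
| Day 4 | 98–106 | 108–114 | 0 of 63 |
| Day 5 | 97–105 | 107–113 | 1 of 63 |
| Day 6 | 96–104 | 106–112 | 6 of 63 |
| Day 7 | 95–103 | 105–111 | 15 of 63 |

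With the implant on Day 4, the regular visit is at most 4 days from target and Day 2 at least 6. If the Week 15 visit is missed, Day 2 can fill the window. A Week 16 retreatment cannot reach the Week 20 window, which opens on day 120.

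**Week 24.** Only a late second implant gets there. Footnote b of SAP Table 4-5 describes regularly scheduled visits as those not shaded grey, and the Cycle 2 visits are the grey ones. Protocol 8.4.3.7 gives late Cycle 2 at an unscheduled visit. Read this way, the regular Week 24 visit always wins when it exists.

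If Day 2 is instead classed as scheduled, it displaces a regular visit on day w when |d − 165| < |w − 165|, or when the two are equal and d is later. The protocol asks that the administration not fall on a regular visit day, so d = w + 1 is left out.

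| Regular Week 24 visit, day w | Day 2 dates that displace it | Number |
|---|---|---|
| 158 | 160–172 | 13 |
| 161 | 163–169 | 7 |
| 165 | none | 0 |
| 169 | 162–168 | 7 |

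Over all in-window visit days with the first implant on Day 4, that is 32 of 234 date combinations. These are counts of dates, not probabilities. If the regular visit is missed, all 28 dates in 151–178 qualify under either reading.

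**Cover from SAP 10.4.5.** A Day 2 reading in 151–178 requires a second implant on days 150–177. Day 150 closes the Week 20 window and days 151–177 lie in the Week 24 window. The implant also precedes the reading. Every such Week 24 value therefore meets the exclusion rule.

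**Size.** Shift = share of patients affected × extra drop. Both inputs are assumptions: 0.5–3% (about 1 to 4 of 144) and 2–6 mm Hg. The range runs from 0.005 × 2 = 0.01 to 0.03 × 6 = 0.18 mm Hg. On the plan's inputs the paired SD is 4 × √(2 × (1 − 0.5)) = 4, and the standard error is 4/√144 = 0.33 mm Hg.

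**The case for a change.** The best case for a change is that the visit variable of a primary endpoint should be stated, not inferred, and that three sentences would do it. The wording on scheduled visits can be read both ways, since Cycle 2 Day 2 is a column in the visit schedule and a Day 2 entry appears in the Hour 0 row of Table 17-1. Table 17-2 gives the reading its own row, but nothing says that a reading may be assigned only once.

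The direction of any error is also predictable. Suppose the regular visit is on day 161, the second implant on day 164 and Day 2 on day 165. If Day 2 counts as scheduled, the pre-implant value is discarded for the next-day one. SAP 10.4.5 removes it only in a sensitivity analysis, and the flexible-regimen repeat in SAP 12.1 concentrates such patients in a smaller sample.

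What stands is that no sentence expressly excludes the reading, and that it can enter Week 24 when the regular visit is missed or Day 2 is classed as scheduled. The doubt about the block does not survive, because the alternative would put Week 24 at about Week 40. Weeks 15 and 20 are summarised only descriptively as secondary endpoints. They also feed the time-weighted average and the imputation, but no noninferiority decision is made at either.

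**Conclusion.** This is a gap that analysts will fill sensibly, and no change to the plan follows. The first-implant clock is the only one compatible with the visit labels, the primary lock and SAP 10.4.5. On the natural reading of scheduled visits, the Day 2 reading can reach the primary analysis only through a missed Week 24 visit combined with a second implant on days 150–177. On the less natural reading, it also displaces the regular visit on a limited set of dates.

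In either case the prespecified SAP 10.4.5 analysis, which uses the primary model, removes every such Week 24 value, so its agreement with the primary result would show whether these readings mattered.

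The 0.01–0.18 mm Hg shift rests on an assumed frequency and an assumed drop, neither of which the documents give. Its upper end is about half a standard error and 12% of the 1.5 mm Hg margin. Naming the first-implant windows, and leaving out readings from later administration days and their Day 2 visits, fits in the programming specification.

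### SAP Table 17-4 puts days 448 to 451 in two visit windows and misses the midpoint cuts of the sister tables, and the 17.3 text conflicts with Table 17-1 on optic disc, ophthalmoscopy and lens data

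*SAP*

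**What the plan says.** **Windows.** Table 17-4 has four post-baseline analysis rows, with targets 165 (Week 24), 361 (Week 52), 537 (Month 18) and 717 (Month 24). The quotes here leave off closing brackets.

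- Week 24 ends at day 267: "administration, Day 1+1, 267"
- Week 52: "Week 52 | 361 | [268, 451"
- Month 18: "Month 18 | 537 | [448, 627"
- Month 24: "Month 24 | 717 | >627"

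**Selection rules.** Section 17.3 prefers a scheduled visit to an unscheduled one in the same window. It then says: "If multiple visits are eligible for windowing within a single visit window, the scheduled visit closest to target day will be used". Two visits equally far from a target are resolved in favour of the later. All of these rules choose among visits inside one window.

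**Routing.** Table 17-1 sends only visual field to Table 17-4. Its row for optic disc, ophthalmoscopy and lens reads "Baseline, W12, W24, W40, W52, M16, M20, M24/EXIT | Table 17-3". The paragraph below it says that Table 17-4 covers visual field and also "ophthalmoscopy, optic disc, and lens assessments which occur every 6 months". The same paragraph lists optic disc under Table 17-3 as well.

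**The concern.** A windowing table should give each assessment day one home. Here four days have two, and two of the three cuts sit away from where the neighbouring tables would put them. A visual field on an overlap day leaves the programmer to choose a rule, and a literal program can enter the same field in both the Week 52 and the Month 18 row.

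The routing conflict matters more. Optic disc and lens are examined at seven post-baseline visits, and Table 17-4 has four post-baseline rows. Sections 11.3.8 and 11.3.9 ask for these summaries by visit and by analysis cycle, and Table 17-4 has no Cycle 2 rows. At stake are the by-visit safety summaries, and a programming choice that would be made on unmasked data if it is not settled in the plan.

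**Working it through.** **1. The convention in the other tables.** The SAP states no midpoint rule, so it has to be inferred. For adjacent targets a and b, let m = (a + b)/2. The earlier window ends on the last whole day before m, and the later one starts on the first whole day at or after m. A midpoint that is a whole day therefore goes to the later visit. For example, Months 16 and 20 in Table 17-3 give (477 + 597)/2 = 537, and the later window does start there: "Cycle 1 Month 20 | 597 | [537, 656". The rule reproduces:

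- Table 17-2, Cycle 1: 20 of 20 boundaries
- Table 17-2, Cycle 2: 20 of 20
- Table 17-3, Cycle 1: 7 of 7
- Table 17-4: 0 of 3

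**2. Table 17-4 against that convention.**

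| Targets | Midpoint | Convention (ends / starts) | Table 17-4 (ends / starts) | Effect |
|---|---|---|---|---|
| 165, 361 | 263 | 262 / 263 | 267 / 268 | Days 264–267 go to Week 24 though nearer Week 52 |
| 361, 537 | 449 | 448 / 449 | 451 / 448 | Windows overlap |
| 537, 717 | 627 | 626 / 627 | 627 / 628 | Cut is on the midpoint; only the tie day goes to the earlier visit |

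Overlap: 451 − 448 + 1 = 4 days.

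**3. Which visual fields can land there.** Table 17-1 schedules fields at Weeks 24 and 52 and Months 18 and 24. The overlap falls in the Month 15 visit range (447 ± 4, days 443–451), when no field is scheduled. Protocol 8.9 has patients who leave early complete the Month 24/Exit procedures, and Protocol Table 6 includes a visual field among them. An early exit or an unscheduled test can therefore produce a field on these days.

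**4. When such a field enters both rows.**

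- Exit on day 450, Week 52 field present: the field at about day 361 is closer to the Week 52 target, so the exit field fills Month 18 only.
- Exit on day 450, no other field in the Week 52 window: the exit field is the only candidate in both windows and enters both rows.
- Unscheduled field on day 450, scheduled Week 52 and Month 18 fields present: it enters neither row.

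Double entry needs an eye with no preferred field in either window.

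**5. Effect of following the text on routing.** Pass the scheduled optic disc and lens days through Table 17-4:

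| Visit | Target day | Table 17-4 row | Days from that row's target | Kept? |
|---|---|---|---|---|
| Week 12 | 81 | Week 24 | 84 | No |
| Week 24 | 165 | Week 24 | 0 | Yes |
| Week 40 | 277 | Week 52 | 84 | No |
| Week 52 | 361 | Week 52 | 0 | Yes |
| Month 16 | 477 | Month 18 | 60 | One of these two |
| Month 20 | 597 | Month 18 | 60 | One of these two |
| Month 24 | 717 | Month 24 | 0 | Yes |

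Seven visits into four rows loses 7 − 4 = 3: Weeks 12 and 40, and one of Months 16 and 20. The survivor of that pair is labelled Month 18, when neither examination is scheduled (Protocol Table 6). With the permitted ±4 days at Month 16 and ±7 at Month 20, the distances to day 537 run from 56 to 64 and from 53 to 67, so either can be kept. Table 17-3 gives each of the seven visits its own row.

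**6. Which routing the rest of the SAP supports.** The visit lists in 11.3.7 (ophthalmoscopy) and 11.3.9 (lens) match Table 17-1. Table 17-3 footnote c treats optic disc as belonging to that table. Only the visual field schedule matches the rows of Table 17-4.

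**The case against.** The best defence is that these are drafting slips with little reach. Much of it stands.

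- A reader might infer that every field on days 448–451 is counted twice. The selection rules prevent that unless the eye has no preferred field in either window.
- A reader might infer that fundus examinations would also drop out of by-visit tables. Section 11.3.7 plans no by-visit table for ophthalmoscopy; it counts eyes with a finding at one or more post-baseline visits. Section 17.5 keeps all post-baseline assessments for safety evaluation and in the listings.
- A reader might infer that Month 20 would always be the visit relabelled Month 18. That follows from the tie rule only if both visits fall exactly on their target days.
- Table 17-1 is the explicit lookup table and most of the SAP agrees with it, so a programmer would probably not follow the stray sentence. The loss of 3 of 7 visits is what happens under the less likely reading.
- The midpoint convention is inferred, and moving the 267/268 cut changes no scheduled field, since those fall within 4 days of days 165 and 361.

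What the defence does not remove is that one day sits in two windows with no rule to resolve it, and that two statements in the same section route the same data differently.

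**Conclusion.** The point holds as a correction to stated analysis rules, at low severity. Table 17-4 has a 4-day overlap without a resolving rule. Two of its bounds miss the midpoints, and its third cut differs only in which side gets the tie day. The 17.3 text conflicts with Table 17-1 on ophthalmoscopy and lens, and with both Table 17-1 and itself on optic disc. If the text were followed, by-visit optic disc and lens summaries would lose 3 of 7 post-baseline visits and would have no Cycle 2 windows.

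The documents do not support reading this as a threat to the efficacy result: Hour 0 IOP uses Table 17-2, whose checked boundaries are consistent. They also give no basis for counting affected eyes, beyond the fact that the overlap can reach only early-exit or unscheduled visual fields.

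Two assumptions are made. The midpoint convention is inferred from Tables 17-2 and 17-3. Days in Table 17-4 are taken to count from the first Bimatoprost SR administration, as in those tables, because its four targets equal theirs.

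**What to change.** 1. Reset Table 17-4, which removes the overlap, leaves no gap and matches Tables 17-2 and 17-3 on all three cuts:
   - Week 24: [first administration Day 1+1, 262]
   - Week 52: [263, 448]
   - Month 18: [449, 626]
   - Month 24: >626
2. Edit the 17.3 paragraph so that Table 17-4 covers visual field only, and optic disc, ophthalmoscopy and lens use Table 17-3.
3. Extend Table 17-3 footnote c, which removes the Week 4 row for optic disc, to ophthalmoscopy and lens. Table 17-1 gives none of the three a Week 4 visit.

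The cost is six bounds, one paragraph and one footnote in a SAP amendment, plus a check that any existing programs follow Table 17-1. No visit, measurement or efficacy analysis changes.
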